Appendix A: Imputation Algorithm for Partial and Missing Dates

Adverse Events

- If the onset date is completely missing, then the onset date is set to date of administration of study drug.
- If year is present and month and day are missing:
 - If year = year of administration of study drug, then set onset month and day to month and day of administration of study drug
 - If year < year of administration of study drug, then set onset month and day to December 31st.
 - If year > year of administration of study drug, then set onset month and day to January 1st.
- If month and year are present and day is missing:
 - If year=year of administration of study drug and
 - If month = month of administration of study drug then set day to day of administration of study drug

- If month < month of administration of study drug then set day to last day of month
- If month > month of administration of study drug then set day to 1st day of month
- If year < year of administration of study drug then set day to last day of month
- If year > year of administration of study drug then set day to 1st day of month
- For all other cases, set onset date to date of administration of study drug

Concomitant Medications

- If start date is completely missing then start date will not be imputed.
- If year is present and month and day are missing then set start month and start day to January 1.
- If start year and start month are present and start day is missing then set start day to 1st day of month.
- If end date is completely missing then end date will not be imputed.
- If year is present and month and day are missing then set end month and end day to December 31.
- If end year and end month are present and end day is missing then set end day to last day of the month.

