3.2.1 Screening Period

After a subject has provided written informed consent, and within 30 days before DTX101 infusion (Day 0), the investigator or other qualified study personnel will determine if the subject is eligible for the study. This will be accomplished by reviewing the inclusion and exclusion criteria and completing all of the screening assessments outlined in the Schedule of Events (Table 15–1). The screening assessments may be performed on more than 1 day, provided that all of the assessments are completed and the results are available within the 30-day screening window and prior to Day 0.

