9.1. Adverse Events

Adverse event terms recorded by the clinical site will be mapped to PT using MedDRA, (version18.1). Severity/toxicity grade will be defined according to the NCI CTCAE v4.03.

An AE is defined as any untoward medical occurrence in a subject enrolled into this study (from the time the subject signs the ICF until their exit from the study) regardless of its causal relationship to study treatment. A TEAE is defined as any event not present before exposure to study product or any event already present that worsens in severity or increases in frequency after exposure to study product.

The relationship of TEAE to study product is categorized as “unrelated”, “possibly related”, “probably related”, or “definitely related”. For summaries by relationship, AEs with a missing relationship are considered to be “possibly related”. For summaries by CTCAE grade (grade 1, grade 2, grade 3, grade 4, and grade 5), AEs missing a CTCAE grade are considered to be CTCAE grade 3. If AE start date is missing, it will be imputed as shown in [Appendix A](#).

The overall number of TEAEs will be summarized for the following:

- All TEAE,
- All serious TEAEs,
- All TEAEs with grade ≥ 3
- All study product related TEAEs,
- All study product related TEAEs \geq grade 3,
- All study product related serious TEAEs,
- TEAEs leading to study discontinuation,
- Any TEAE leading to death.

The total number, the frequency, and the percentage of subjects with TEAEs will be tabulated by dosage, SOC, and PT for the following:

- TEAEs,
- Serious TEAEs,
- TEAEs by relationship,
- TEAEs resulting in study discontinuation,
- TEAEs by severity,
- Related TEAEs,
- Related serious TEAEs,
- TEAEs grade ≥ 3 ,
- All study product related TEAEs/Serious TEAEs (DLT) \geq grade 3.

At each level of summarization, a subject will be counted only once (with the strongest relationship and the greatest severity) for each TEAE he experiences within that level. Data listings will be provided for all TEAEs.

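### SAP Appendix A imputes AE onset without looking at the end date, so an event that ended before dosing can be given a later onset and may be counted as treatment-emergent

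*SAP*

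**What the plan says.** SAP section 9.1 sends incomplete AE start dates to the appendix: "If AE start date is missing, it will be imputed as shown in" Appendix A. Four branches there give the dosing date as onset:

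- date wholly missing: "If the onset date is completely missing, then the onset date is set to date of administration of study drug";
- only the year known: "If year = year of administration of study drug, then set onset month and day to month and day of administration of study drug";
- day missing: within the dosing year, "If month = month of administration of study drug then set day to day of administration of study drug";
- catch-all: "For all other cases, set onset date to date of administration of study drug".

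None of these depends on when the event ended. Section 9.1 collects AEs "from the time the subject signs the ICF until their exit from the study", and Protocol section 3.2.1 allows up to 30 days between screening and infusion. Protocol section 9.1.2.1 has the site record the time of resolution. Treatment emergence is defined in words, not by dates: "A TEAE is defined as any event not present before exposure to study product or any event already present that worsens in severity". The same sentence also covers events that become more frequent once the subject has been dosed. TEAE incidence by cohort is part of the first primary endpoint (Protocol section 10.2, SAP Table 2-1).

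**The concern.** Setting an unknown onset to the dosing day is a sensible conservative default when nothing shows that the event came earlier. A recorded end date before dosing does show that, and the rule overrides it. The first result is an impossible record, with an onset after the event was over. The second, if the program classifies TEAEs by comparing imputed onset with the dosing date, is a pre-dose event in the treatment-emergent tables. Every AE table listed in SAP section 9.1 is a TEAE table, and cohorts have 3 subjects, so one such event can be visible in the result for a dose.

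**Working it through.** The plan states no figure on this point, so there is none to reproduce. The check applies the rules as written.

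**Inputs.** Date rules: SAP Appendix A. Pre-dose window: Day -30 to Day -1 (Protocol section 3.2.1 and Table 15–1). Subjects per dose: 3 per cohort, with 3 more at the OBD, so 6 at that dose and 3 × 3 + 3 = 12 in all (SAP section 4.4). Assumptions: an illustrative calendar year (2016, 366 dosing dates), and equal weight for every possible onset and end pair.

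**Single cases.** Dosing 20 March 2016, event ended 10 March 2016:

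| Onset as recorded | Imputed onset | Result |
|---|---|---|
| missing | 20 March 2016 | dosing day, 10 days after the end |
| 2016 | 20 March 2016 | same |
| March 2016 | 20 March 2016 | same |
| February 2016 | 29 February 2016 | before dosing, consistent with the end date |

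**All cases with onset and end both before dosing.** An onset k days before dosing (k = 1 to 30) has k possible end days, so there are 30 × 31 / 2 = 465 pairs per dosing date, and 366 × 465 = 170,190 in total. The share given a dosing-day onset is:

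- Onset wholly missing: 170,190 / 170,190 = 100%.
- Year only: the exceptions are onsets in the previous year. An onset k days before dosing falls in 2015 for the first k dosing dates of January, so the exceptions number the sum of k × k for k = 1 to 30, which is 9,455. The share is (170,190 − 9,455) / 170,190 = 94.4%.
- Day missing: a month of L days gives (L − 1) × L × (L + 1) / 6 pairs with onset in the dosing month. Seven months of 31 days, four of 30 and one of 29 give 7 × 4,960 + 4 × 4,495 + 4,060 = 56,760. The share is 56,760 / 170,190 = 33.4%.

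Each of these events has an onset later than its own end, because the end is Day -1 at the latest. The rules that choose 31 December or the last day of an earlier month also produce onset after end. Counting those, the shares with onset after end are 97.1% (year only) and 65.0% (day missing). The additional events stay before dosing, so their TEAE status is not affected.

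These percentages are conditional on an event having ended before dosing and having that pattern of missing date. They are not expected frequencies; the documents give none.

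**With the end date used.** Taking onset as the earlier of the imputed onset and the end date, 0 of 170,190 events fall on or after the dosing date under any of the three patterns.

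**Effect on incidence.** One extra subject counted adds 1/3 = 33.3 points at a dose with 3 subjects, 1/6 = 16.7 with 6, and 1/12 = 8.3 over 12 subjects. If the subject already has a TEAE at that level of the table, the change is 0, because subjects are counted once per level (SAP section 9.1).

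**Comparison within the SAP.** For a medication with a wholly missing start and an end before Day 0, SAP section 7.1 uses the end date and classes it as prior. The AE rule, facing the same information, does not.

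**The case against.** The strongest reply is that the TEAE definition already settles the matter. An event recorded as ended before dosing was present before exposure and cannot worsen afterwards, so by the written definition it is not a TEAE, whatever onset is imputed. Neither document says that status is derived from the imputed onset. This stands as a limit: a reader might infer that every such event is certainly miscounted, and the documents do not support that. The impossible onset date remains on either reading, and the SAP gives the programmer no rule for choosing between the definition and the imputed date.

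The case also needs several things together: a pre-dose AE, an onset that is missing or partial in the ways above, and a known earlier end. The protocol asks for all eCRF items to be completed and queries resolved before lock (sections 10.6 and 10.6.1), and with 12 to 18 subjects an onset after its end would show in the listings. The error over-counts, and safety analyses are descriptive. All of this stands and keeps the point minor. The over-count is not a reason to keep the rule, since the end date removes the uncertainty that a conservative default is meant to cover.

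Three further readings are tempting and go too far:

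- That one event always adds 33 points to a cohort's incidence. That is a maximum, likely mainly in individual SOC or PT rows, since a subject followed for 52 weeks may well have another TEAE.
- That the rule feeds false DLTs into dose finding. Section 9.1 treats a missing relationship as possibly related and a missing grade as grade 3, but for summaries. An event would need those items missing as well to reach the related grade 3 or higher table. The DLT definition in SAP section 3.1.2 rests on the investigator's own judgement of relatedness.
- That the screening FIX washouts make the case common. They apply only to prophylaxis subjects without a documented FIX history (Protocol section 3.2.3.1), and nothing links them to missing AE dates.

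**Conclusion.** The rule is wrong as written, and the point is minor. It is certain that Appendix A can assign an onset after the recorded end of an event that was over before dosing. That such an event is then counted as treatment-emergent depends on the program using the imputed onset, which is the natural reading but not a stated one. If it does, the effect on a dose's TEAE incidence is at most 33 percentage points with 3 subjects and 17 with 6, and nothing where the subject already has a TEAE at that level. The case is expected to be rare, though the documents give no rate of missing AE dates. Partial onsets in an earlier month or year are already placed before dosing.

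**What to change.** Add three statements to the AE part of Appendix A:

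1. An AE whose end date, or the known part of it, shows that it ended before DTX101 administration is not treatment-emergent.
2. An imputed onset may not be later than a complete AE end date.
3. If the end date is missing, or is partial and does not establish that the event ended before dosing, the existing conservative rule stays.

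Statement 1 settles TEAE status however the program derives it and brings AEs into line with SAP section 7.1. Statement 3 is needed because Appendix A has no rule for partial AE end dates: an end recorded only as 'March', with dosing on 15 March, proves nothing either way. Where a partial end date does settle the matter, the listing can show the onset as recorded.

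The cost is a few lines in the SAP and in the program. No new data are needed, and nothing in the conduct of the trial changes.

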Appendix B: Schedule of study

Procedure	Period	Screening	Dosing	Treatment Period: Week 2 through Week 52 (includes clinic or home visits [see Error! Reference source not found.])								Unscheduled	End of Study/Early Withdrawal	
				Days -30 to -1	Day 0	2	4	6	8	10	12	16-48 ^a		
	Visit Window (Days)	-	-	± 2	± 2	± 2	± 2	± 2	± 2	± 2	± 4	-	± 7	
Informed consent		X												
Demographics		X												
Medical history		X												
Hemophilia history		X												

Procedure	Period	Screening	Dosing	Treatment Period: Week 2 through Week 52 (includes clinic or home visits [see Error! Reference source not found.])								Unscheduled	End of Study/Early Withdrawal	
				Days -30 to -1	Day 0	2	4	6	8	10	12	16-48 ^a		
	Week	Visit Window (Days)	-	-	±2	±2	±2	±2	±2	±2	±4	-	±7	
Prior medication / therapies / procedures		X												
Review of eligibility criteria		X												
FIX genotyping		X												
HLA genotyping		X												
HBV, HCV, and HIV status		X												
FIX inhibitor (Bethesda assay)	X	X ^b				X	X				X ^c	X ^d	X	
Coagulation panel (PT/INR, D-dimer assay, aPTT)	X	X ^b	X	X	X	X	X	X	X	X	X ^d		X	
AAVrh10 neutralizing antibody test (ELISA)	X	X ^b				X	X				X ^c	X ^d	X	
Cell-mediated immune response to AAVrh10 and FIX (ELISPOT assay)		X ^b				X	X				X ^c	X ^d	X	
AAVrh10 binding antibody IgG assay (ELISA)	X	X ^b				X	X				X ^c	X ^d	X	
Saliva, urine, and stool for viral shedding (qPCR) ^f		X ^e	X	X	X	X	X	X	X	X	X ^d		X	
FIX activity (aPTT clot-based assay)	X	X ^b	X	X	X	X	X	X	X	X	X ^d		X	
Hematology / clinical chemistry ^g	X	X ^h	X	X	X	X	X	X	X	X	X ^d		X	

Procedure	Period	Screening	Dosing	Treatment Period: Week 2 through Week 52 (includes clinic or home visits [see Error! Reference source not found.])								Unscheduled	End of Study/Early Withdrawal
				Days -30 to -1	Day 0	2	4	6	8	10	12	16-48 ^a	
	Week	Visit Window (Days)	-	-	±2	±2	±2	±2	±2	±2	±4	-	±7
Urinalysis	X		X	X	X	X			X			X ^d	X
12-lead ECG	X	X ⁱ											X
Vital sign measurements (heart rate, blood pressure, respiratory rate)	X	X ^j	X	X	X	X	X	X	X	X	X	X	X
Height and weight ^k	X	X ^{b, l}											X ⁱ
Complete physical examination	X												X
Targeted physical examination ^m		X ^b				X				X	X ⁿ		
AE/SAE monitoring	X	X	X	X	X	X	X	X	X	X	X	X	X
Concomitant medications / therapies / procedures		X ^b	X	X	X	X	X	X	X	X	X	X	X
Diary distributed		X											
Diary reviewed			X	X	X	X	X	X	X	X	X	X	X
Diary returned													X
Record of spontaneous bleeding episodes	X	X ^b	X	X	X	X	X	X	X	X	X	X	X
Record recombinant FIX use	X	X ^b	X	X	X	X	X	X	X	X	X	X	X
Prophylactic recombinant FIX washout	X ^o					X ^{p, q}					X ^{r, s}		X ^{r, s}
EQ-5D-5L QoL questionnaire		X ^b									X ⁿ		X

Procedure	Period	Screening	Dosing	Treatment Period: Week 2 through Week 52 (includes clinic or home visits [see Error! Reference source not found.])							Unscheduled	End of Study/Early Withdrawal
	Week	Days -30 to -1	Day 0	2	4	6	8	10	12	16-48 ^a		52
	Visit Window (Days)	-	-	±2	±2	±2	±2	±2	±2	±4	-	±7
Haem-A-QoL questionnaire		X ^b								X ⁿ		X
DTX101 infusion		X										

Abbreviations: AAVrh10, adeno-associated virus serotype rh10; AE, adverse event; aPTT, activated partial thromboplastin time; ECG, electrocardiogram; ELISA, enzyme-linked immunosorbent assay; ELISPOT, enzyme-linked immunospot; EQ-5D-5L, EuroQoL 5D 5 level; FIX, factor IX; Haem-A-QoL, Haemophilia-Specific Quality of Life; HBV, hepatitis B virus; HCV, hepatitis C virus; HIV, human immunodeficiency virus; HLA, human leukocyte antigen; IgG, immunoglobulin G; INR, international normalized ratio; PT, prothrombin time; QoL, quality of life; qPCR, quantitative polymerase chain reaction; SAE, serious adverse event.

- Following the Week 12 visit, subjects will return to the study site once every 4 weeks starting at Week 16.
- To be collected before DTX101 administration.
- Samples to be obtained at Weeks 16, 32, 40, and 48.
- A laboratory parameter may be repeated if there is any concern about the values obtained. Laboratory values must be repeated if ≥ 2 -fold the upper limit of normal or ≤ 0.5 -fold the lower limit of normal.
- Saliva and urine samples for viral shedding to be collected before DTX101 administration. Subjects will be provided with an appropriate container to collect a stool sample at home prior to the visit.
- Samples for viral shedding to be collected at Weeks 2, 4, 6, 8, 10, and 12 and on Days 8, 20, 36, 48, 64, and 76 (see Error! Reference source not found.) until negative on 3 consecutive occasions for each sample matrix.
- Hematology to include: complete blood count and differential. Clinical chemistry to include: sodium, potassium, chloride, carbon dioxide, blood urea nitrogen, creatinine, glucose, calcium, phosphate, magnesium, albumin, total protein, creatine kinase, bilirubin (total and indirect), alanine aminotransferase, aspartate aminotransferase, alkaline phosphatase, gamma-glutamyl transferase, and lactate dehydrogenase.
- Samples for clinical laboratory assessments to be collected before DTX101 administration and 0.5, 4, and 8 hours after the start of the infusion.
- A 12-lead electrocardiogram to be performed in triplicate before the start of infusion. A single 12-lead electrocardiogram to be performed 1 hour after the start of the infusion. The ECGs should be measured with the subject in a semi-supine or supine position, having rested in this position for at least 5 minutes beforehand.
- Vital signs to be measured at predose, at 5 minutes after the start of the infusion, and at 0.5, 1, 2, 4, 6, and 8 hours after the start of infusion (± 5 minutes). The predose measurement of heart rate and blood pressure is to be performed in triplicate, with measurements taken 2 minutes apart. Vital signs will also be measured at 22 hours (± 1 hour) after the start of infusion, prior to subject discharge. Vital signs

should be measured with the subject in a semi-supine or supine position, having rested in this position for at least 5 minutes beforehand.

- k. Height to be collected at screening only.
- l. Only weight to be collected.
- m. Targeted physical examination to include assessment of the skin and the respiratory, cardiovascular, and gastrointestinal systems.
- n. To be recorded at Weeks 24, 36, and 48.
- o. This is only applicable if a subject does not have a documented history of FIX activity and a baseline sample is needed to confirm severity of hemophilia B. For subjects taking long-acting recombinant FIX prophylactically, washout is to start at Day -28 and last at least 21 days (Day -7). For subjects taking traditional recombinant FIX prophylactically, washout is to start at Day -14 and last at least 7 days (Day -7). The baseline sample must be obtained and results available prior to dosing on Day 0.
- p. For subjects who take long-acting recombinant FIX prophylactically, start washout at Week 3 for the Week 6 FIX measurement.
- q. For subjects who take traditional recombinant FIX prophylactically, start washout at Week 5 for the Week 6 FIX measurement.
- r. For subjects who continue to take long-acting recombinant FIX prophylactically, start washout at Week 21 for the Week 24 FIX measurement and again at Week 49 for the Week 52 FIX measurement.
- s. For subjects who continue to take traditional recombinant FIX prophylactically, start washout at Week 23 for the Week 24 FIX measurement and again at Week 51 for the Week 52 FIX measurement.

Appendix C: List of Protocol Deviations
